# Incomplete Concomitant Medication Start Date

If year is missing (or completely missing): do not impute.

If (year is present and month and day are missing) or (year and day are present and month is missing):

Set *month* and day to January 1st.

If year and month are present and day is missing:

Set day to 1st day of month.

#### **Incomplete Concomitant Medication End Date**

If *year* is missing (or completely missing): do not impute.

If (year is present and month and day are missing) or (year and day are present and month is missing):

Set month and day to December 31st.

If year and month are present and day is missing:

Set day to last day of the month.

#### Incomplete Subsequent Anti-Cancer Therapy Start Date

Assumption: Anti-Cancer therapies reported on the Subsequent Anti-Cancer Therapy CRF. If *year* is missing (or completely missing): set to date of last dose of study treatment + 1 If (*year* is present and *month* and *day* are missing) or (*year* and *day* are present and *month* is missing):

If year > year of the last dose: Set *month* and day to January 1st.

If year = year of the last dose: Set month and day to date of last dose of study treatment + 1 If year and month are present and day is missing:

Set *day* to 1st day of month if the resulting imputed date is greater than date of last dose or if the month is before the month of last dose date and year is same or before the year of the last dose date. Otherwise set the imputed date to date of last dose + 1

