### **3.6 Discontinuation and Withdrawal**

#### **3.6.1 Treatment Discontinuation**

Subjects will receive study treatment until treatment discontinuation for any of the reasons listed below. Subjects may discontinue study treatment at any time without prejudice. If a subject discontinues study treatment, the reason will be documented in source documents. However, the subject will continue to be followed for safety as described in Section 5.5.1 and survival as described in Section 5.5.2; for subjects who discontinue study treatment prior to disease progression, disease assessments and HRQOL assessments should continue per the protocol-defined schedule (Section 5.5.2). For subjects who discontinue study treatment, every effort must be made to continue protocol-specified evaluations and follow-up (Appendix A; Appendix B [Open-Label Phase]) unless the subject also withdraws consent to participate in all aspects of the study (see Section 3.6.2). Subjects who request to discontinue study procedures, may consent to allow follow-up for survival. Otherwise, all subjects will be followed until death or until a decision by the Sponsor is made to stop collection of these data.

The following are possible reasons for discontinuation from study treatment:

- Subject no longer experiences clinical benefit as determined by the investigator. If study treatment is withdrawn for this reason, the date of this decision is to be recorded and every effort should be made to continue safety evaluations and collection of subsequent treatment information and follow-up information for survival.
- Unacceptable side effects the investigator feels may be due to study treatment, including any subject with a GI or non-GI perforation/fistula
- The investigator feels it is not in the best interest of the subject to continue on study

- Participation in another clinical study using an investigational agent or investigational medical device
- Necessity for treatment with nonprotocol systemic anticancer therapy
- Receipt of liver-directed local anti-cancer therapy (eg, transarterial tumor embolization or chemoembolization, radiofrequency or microwave ablation, percutaneous ethanol or acetic acid ablation, injection or infusion of drug eluting or radiation-emitting beads, cryoablation, radiation therapy, including stereotactic radiotherapy, or surgery)
- Necessity for withholding study drug for greater than 6 weeks for AEs, unless continuation of treatment is approved by the Sponsor

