# 4.4 Missing and Partial Data

In general, other than for partial dates, missing data will not be imputed and will be treated as missing. The algorithms for imputation of partial dates vary depending upon the parameter. These are presented in Appendix A.

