# 7.2.1 Progression-Free Survival (PFS)

#### 7.2.1.1 Definition

Duration of PFS is defined as the time from randomization to the earlier of the date of radiographic progression or date of death due to any cause.

PFS (months) =(earliest date of progression, death, censoring – date of randomization + 1)/30.4375

The primary analysis of PFS will include all subjects in the ITT population and will include radiographic progression events as determined by the investigator per RECIST 1.1 and deaths.

The recorded date of radiographic progression is the date of the tumor assessment visit at which progression is declared. If multiple scan dates are associated with a tumor assessment visit, the earliest assessment date within the set will be chosen as the progression date.

Only adequate tumor assessments (ATAs) will be considered in the determination of radiographic progression and censoring dates. For the purpose of this study, ATA is defined as one that results in a time point assignment of: response (complete or partial), stable disease/(non-CR, non-PD), or progression. For PFS, ATA is based on soft tissue evaluation by CT/MRI and/or new lesions identified by bone scan.

General censoring rules for the primary analysis of PFS are described below:

• Subjects who receive systemic or liver directed local NPACT or non-protocol radiation therapy (other than to bone) or surgery to resect tumor lesions before experiencing an

event will be right censored at the date of the last ATA on or prior to the date of initiation of subsequent therapy/surgery. If there is no such tumor assessment after randomization, the subject will be right censored on the date of randomization.

- Subjects who have not experienced an event (and are not otherwise censored) at the time of data cutoff will be right censored on the date of their last tumor assessment after randomization that is on or prior to the data cutoff. If there is no such tumor assessment after randomization, the subject will be right censored on the date of randomization.
- Subjects who miss two or more ATAs (operationally defined as 126 days without an ATA) followed by an event (progression or death) will be right censored on the date of their most-recent ATA prior to the missing assessments. If there is no such tumor assessment after randomization, the subject will be right censored on the date of randomization

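### Imputed start dates for subsequent therapy ignore a documented progression, so in probably a few subjects at most a PFS event can become an earlier censoring

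*SAP*

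**What the plan says.** SAP Appendix A (Incomplete Subsequent Anti-Cancer Therapy Start Date) has these branches:

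- Year missing: "set to date of last dose of study treatment + 1".
- Month missing, year equal to the year of last dose: "Set month and day to date of last dose of study treatment + 1".
- Month missing, later year: 1 January of that year.
- Day missing: the 1st of the month if that is after last dose, or if the recorded month is before the month of last dose. Failing both, "Otherwise set the imputed date to date of last dose + 1".

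SAP 4.4 sends all partial dates to this appendix: "The algorithms for imputation of partial dates vary depending upon the parameter". There is no separate rule for PFS.

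SAP 7.2.1.1 provides that a subject who starts systemic or liver-directed therapy before a PFS event is "right censored at the date of the last ATA on or prior to the date of initiation of subsequent therapy/surgery", or at randomization if there is no such assessment (ATA, adequate tumor assessment).

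Protocol 3.6.1 keeps imaging going after drug is stopped: "for subjects who discontinue study treatment prior to disease progression, disease assessments and HRQOL assessments should continue per the protocol-defined schedule".

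**The concern.** Whether a progression counts in the primary PFS analysis depends on which came first, progression or new therapy. With a partial date that order may be unknown, and the appendix settles it without consulting the progression date on file. Because scans continue off drug, last dose before a documented progression is a situation that the protocol provides for.

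Elsewhere Appendix A does respect known dates. An incomplete death date may not fall before the day after the subject was last known alive, and a dosing start date that lands before an earlier dosing milestone is moved forward. The therapy rule has no such check against progression.

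PFS is tested at two-sided 0.04 once OS is significant. Its event status should not depend on which part of a date a site left blank. The same date also matters elsewhere:

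- PFS3 uses the same censoring.
- PFS2 counts therapy as an event on its start date.
- Best overall response (SAP 7.2.2.1) stops at the PFS censoring events.

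**Working it through.** The plan gives no figure on this point to reproduce: no partial-date rate, and no PFS event count or power. The check applies the written rules to dates.

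**Notation.** L is last dose, P the progression scan, N the true therapy start and I the imputed start. PFS in months = (date − randomization + 1)/30.4375 (SAP 7.2.1.1). Scans are every 8 weeks. If I < P, PFS is censored at the last ATA on or before I.

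**Step 1. When the order is reversed.**

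- Year missing, or month missing in the year of L: I = L + 1. So I < P whenever L is two or more days before P.
- Month missing in a later year: I = 1 January, which is before any P later in that year.
- Day missing, L before P: I is the 1st of the month or L + 1. I < P can then arise when N and P share a calendar month.
- Day missing, recorded month before the month of L: I is the 1st of that month, even if L is after P. Example: P = 12 March, L = 5 April, therapy recorded as March. Then I = 1 March.
- Otherwise, with L on or after P, L + 1 falls after P and the event stands.

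**Step 2. Worked case.** Randomization 5 Jan 2015, last dose 10 Apr, scans without progression on 2 Mar and 27 Apr, progression 22 Jun.

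| Therapy record | True start | Imputed start | Primary PFS as written | PFS2 as written |
|---|---|---|---|---|
| Complete | 12 Jul | none needed | event 22 Jun: 169/30.4375 = 5.55 | event 5.55 |
| Month or whole date missing | 12 Jul | 11 Apr | censored 2 Mar: 57/30.4375 = 1.87 | event 11 Apr: 97/30.4375 = 3.19 |
| Day missing (June) | 28 Jun | 1 Jun | censored 27 Apr: 113/30.4375 = 3.71 | event 1 Jun: 148/30.4375 = 4.86 |

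**Step 3. How often, given that therapy truly followed progression.** The rules were run on 150,000 simulated date sets.

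| Group | Whole date missing | Month missing | Day missing |
|---|---|---|---|
| L 2–56 days before P, N 1–60 days after P | 100% | 92% | 23% |
| L on or after P, N after L | 0% | 0% | 0% |
| L after P, N after P but on or before L | 0% | 0% | 25% |

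Where the event was lost, censoring fell about 56 days before progression on average. A second simulation (L 1–56 days before P) varied the gap from P to N over 0–28, 7–42 and 14–56 days. It gave 50%, 24% and 10% with the day missing, and 94%, 91% and 89% with the month missing.

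**Step 4. Scale.** Every input except the number of subjects is an assumption.

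- Both arms, subjects exposed: 760 × 25% with later therapy × 10–30% stopping before progression × 5–20% with a partial date. Low: 760 × 0.25 × 0.10 × 0.05 = 0.95. High: 760 × 0.25 × 0.30 × 0.20 = 11.4.
- If only the day is missing, at 23%: 0.95 × 0.23 = 0.2 to 11.4 × 0.23 = 2.6 events lost.
- Cabozantinib arm, central case, day missing: 507 × 0.7 with progression × 0.2 off drug first × 0.3 with later therapy × 0.1 partial × 0.24 = 0.5.

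**The case against.** **The link to PFS is inferred.** SAP 4.6 describes imputed medication dates in terms of summary tables, and nothing says outright that they drive PFS censoring. That is fair. But SAP 4.4 is general and no other rule exists, so a programmer would use this one. The silence is itself a reason to clarify.

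**The simulated percentages presuppose the error.** They hold only when therapy truly began after progression. A subject who stopped for toxicity may start new therapy first, and censoring is then what the SAP intends. This stands: the percentages are not error rates among all partial dates.

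**Dates will mostly be nearly complete.** Protocol 5.5.2 asks for contact about every 8 weeks and for therapy dates. A missing day is therefore the likeliest gap, which points to the lower figures. This stands too.

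**The remedy uses the outcome to set a censoring date.** The present rule is prespecified and blind to progression. Bounding it by progression settles ambiguous cases in favour of an event. This is a real trade-off, and the reason to pair the change with a sensitivity analysis.

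**Stronger readings that a reader might infer.**

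- That lost events would favour cabozantinib, because more subjects stop it for toxicity. The documents give no placebo rate of stopping before progression. The 22% adverse-event discontinuation in Protocol 1.3.3.1 comes from single-agent studies and includes disease progression. Placebo subjects may also stop for loss of clinical benefit before a radiographic event.
- That the fault needs last dose to precede progression. The branch for an earlier therapy month is an exception. It requires therapy that overlaps study drug, which Protocol 7.1.2 does not permit, so it should be uncommon.
- That any dose hold creates the problem. A hold matters only if dosing never resumes before progression.

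**Conclusion.** The point holds as a small defect in a written rule. Read literally, Appendix A can place a therapy that followed a documented progression before it, and SAP 7.2.1.1 then replaces the event with an earlier censoring. PFS3 does the same. PFS2 keeps an event but dates it too early. Objective response is affected only if a response or its confirmation falls after the imputed date. None of the planned PFS analyses is free of the problem.

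The number affected is unknown. On the assumptions shown it is about zero to a few subjects; about 11 would need every input at its upper end and the event lost in every exposed subject. The direction between arms is not established, and the PFS conclusion is unlikely to change.

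The exploratory OS analysis in SAP 7.1.4 is not a reason for the change. Progression is not an event there, so the imputation only moves a censoring date, and the day after progression has no special standing.

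**What to change.** Add to SAP Appendix A, for PFS and ORR censoring:

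- When the known parts of the therapy date allow a start after a documented radiographic progression, use the later of the currently imputed date and progression + 1, capped at the end of the recorded month or year.
- Where the year is missing, apply the same rule and add a sensitivity analysis that ignores imputed therapy dates.
- For ITT subjects never dosed, who have no last dose date, use the randomization date in its place.

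The edit should also supply the branch now absent for a missing month in a year before the year of last dose.

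In the worked case the imputed start becomes 23 Jun under all three patterns of missingness, and the event at 5.55 months is restored.

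The cost is a few sentences and one sensitivity analysis, with no new data and no change to conduct. SAP 4.8 provides the route: a revised SAP or an addendum approved before unblinding. The downside is that if therapy truly began before progression within the same partial-date range, that progression is counted as an event instead of being censored.

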#### Incomplete Death Date

Identify date of last known alive (LA) prior to death from the following:

- 1. Date of decision to discontinue study treatment from End of Treatment CRF
- 2. Date of last radiographic assessment from End of Radiographic Follow Up CRF
- 3. Date last known alive from Survival Follow Up CRF
- 4. Date of last lab assessment from the Labs dataset

If year is missing (or completely missing): set to date of LA + 1

If only day is missing: set to the maximum of the first of month or LA + 1

If month and day are missing:

If year of LA = year of death

Set death date to date of LA + 1

If year of most-recent contact < year of death

Set *month* and *day* to Jan 1st.

## Incomplete Study Treatment Start Date

Define previous sequential dosing "milestone" as the latest of previous dose stop date, previous dose hold stop date, date of first dose or randomization date.

If *year* is missing (or completely missing): set to date of previous sequential dosing "milestone" + 1

If (year is present and month and day are missing) or (year and day are present and month is missing): set to January 1st

If year and month are present and day is missing: set to the first day of the month

If the imputed date is before the previous sequential dosing "milestone": set to the date of previous sequential dosing "milestone" + 1

## **Incomplete Study Treatment Stop Date**

Define next sequential dosing "milestone" as the earliest of next dose start date, next dose hold start date, date of last dose from EOT CRF or the cutoff date.

If year is missing (or completely missing): set to date of next sequential dosing "milestone" - 1

If (year is present and month and day are missing) or (year and day are present and month is missing): set to December 31st

If year and month are present and day is missing: set to the last day of the month

If the imputed date is after the next sequential dosing "milestone": set to the date of next sequential dosing "milestone" - 1

# **Appendix B: Rounding Rules for Reported Percentages**

For percentages  $\geq 10\%$ :

- Values  $\geq$  X.5 or above round to X+1.
- Values >X but <X.5 round to X.

For percentages <10%:

- Values  $\geq$  X.Y5 or above round to X.Y+0.1.
- Values >X.Y but <X.Y5 round to X.Y.

# **Appendix C: Imputation Rules for Laboratory Values Outside of Quantification Range**

- Lab values below the lower level of quantification (LLQ) that are reported as "<LLQ" or "\( \leq \text{LLQ} \)" in the database will be imputed by LLQ x 0.99 for analysis purposes. However the original value will also be maintained.
- Lab values above the upper level of quantification (ULQ) that are reported as ">ULQ" or ">ULQ" in the database will be imputed by ULQ x 1.01 for analysis purposes. However the original value will also be maintained.

# **Appendix D: EQ-5D-5L Index Value Conversion Guidelines**

The EQ-index conversion algorithm (EQ-5D-5L User Guide 2.1, April 2015. Available from: http://www.euroqol.org/about-eq-5d/publications/user-guide.html):

- o Calculate *health state* 
  - Each of the 5 dimensions comprising the EQ-5D descriptive system is divided into 5 levels of perceived problems:
    - Level 1: indicating no problem
    - Level 2: indicating slight problems
    - Level 3: indicating moderate problems
    - Level 4: indicating severe problems
    - Level 5: indicating extreme problems
  - A unique health state is defined by combining 1 level from each of the 5 dimensions. For example, state 11111 indicates no problems on any of the 5 dimensions, while state 12345 indicates no problems with mobility, slight problems with washing or dressing, moderate problems with doing usual activities, severe pain or discomfort and extreme anxiety or depression. Note that missing values will be coded as '9'. Ambiguous values will be treated as missing values.
- EQ-index values for each country = health state \* the country specific conversion factors for each dimension (EQ-5D-5L Index Value Calculator, version 1)
